## **VII. Risks and Discomforts**

**Epelerenone:** Adverse drug reactions associated with the use of eplerenone include: hyperkalaemia, hypotension, dizziness, headache, stomach pain, cough, breast enlargement, rash, abnormal vaginal bleeding, erectile dysfunction, and altered renal function. Other rare side effects have been reported include fatigue, chest pain, tingling in arms and legs, loss of muscle tone, weakness or heaviness in legs, confusion, lack of energy, cold, gray skin or irregular heartbeat, and diarrhea. These potential side effects will be assessed for throughout the study. Any subject with serum K >5.5 mEq/L at screen will be excluded from the study. During the study, a subject who has an elevated K of > 5.5 mEq/L at any study visit will have a recheck; if the K remains elevated after recheck they will be excluded from the study. Additionally, subjects who experience symptoms of hyperkalemia and have a K > 5.0 mEq/L will be excluded from continued participation in the study. Subjects who have hypotension (SBP<90) at any study visit after titration to full dose eplerenone 50mg/d will be given a dose reduction to 25 mg/d. If a subject remains hypotensive (SBP <90) or symptomatic of hypotension at the reduced dose they will be dropped from the study. Since patients with renal insufficiency may require reduced dosing based on creatinine clearance, subjects with renal insufficiency (serum creatinine > 1.5 mg/dl) will also be excluded from participation. Concomitant use of full dose ritonavir, nelfinavir, clarithromycin and other strong inhibitors of CYP34A (see Appendix A for complete list) will be an exclusion in the study as will the use of St. John's Wort (CYP3A4 inducer).

**Oral Glucose Tolerance Test:** Subjects may find the 75g glucose beverage distasteful. In addition, there is a possibility of "reactive" hypoglycemia in the latter part of the OGTT or after its conclusion. If subjects develop symptoms of hypoglycemia they will have their blood sugar tested and will be treated appropriately. Subjects will be given a meal immediately following the conclusion of the OGTT.

Randomized placebo-controlled trial to investigate the effects of eplerenone in patients with HIV-associated abdominal fat accumulation

#### Radiation

As a result of participation in this study, subjects will be exposed to 4 DEXA scans over 12 months. The radiation risk associated with the whole body DEXA scan is approximately 0.26 mrem of radiation, for a total of approximately 1 mrem during the study. The total radiation exposure associated with this study does not pose excessive risk to subjects.

Magnetic Resonance Imaging: Subjects will be carefully screened for metal implants such as surgical clips or pacemakers prior to MRI scanning. Subjects will be given earplugs due to the loud noises during the test. Subjects who feel uncomfortable in confined spaces may have difficulty in the narrow cylinder of the MRI, and the MRI can be stopped at any time at the patient's request. There are no known hazards for pregnant women.

Euglycemic Hyperinsulinemic clamp/insulin: Administration of insulin infusion can cause hypoglycemia. Blood sugar will be monitored every 5 minutes during the insulin clamp, and 20% dextrose is infused per protocol to achieve target blood glucose of 90mg/dL. In the event of hypoglycemia, 50% dextrose is available at the bedside, and a physician or nurse practitioner is present throughout the insulin clamp procedure. There is a theoretical risk of infection associated with the use of albumin, a protein purified from donated blood. The risk of transmitting disease is reduced by testing blood donors for infections, and by heat treating and purifying the albumin. The albumin that will be used for the insulin mixture is the same formulation that is commonly used for patients in the hospital and is FDA approved. Because of these measures, the risk is considered to be very small; no cases of disease transmission have ever been identified for albumin.

Blood Drawing: The total blood drawn for subjects completing the study is equivalent to approximately 2 3/4 cups during 12 month period. Patients who have the optional overnight blood sampling will have an additional 3/4 cup of blood drawn. This quantity of blood drawing over 12 months does not pose excessive risk to patients. Patients with a hemoglobin < 11 mg/dL will be excluded from the study. There will be minimal risk and discomfort associated with blood drawing and IV placement. The risks of these procedures are minor bruising or bleeding at the site of the blood draw or IV catheter.

Flow Mediated Vasodilation: There are no known risks of ultrasound measurements. There is the possibility of discomfort from having the blood pressure cuff inflated for 5 minutes, this includes numbness or tingling of the arm.

### **VIII. Potential Benefits**

The potential benefits of this study include improved body composition, cardiovascular health, and improved glucose and insulin metabolism associated with HIV associated metabolic abnormalities. These benefits may be associated with eplerenone, lifestyle modification or both. In addition, all subjects will be provided with tools to help them meet the prescribed goals, including a core curriculum binder. All of the participant educational handouts have been included as attachments to this document.

### **IX. Monitoring and Quality Assurance**

Randomized placebo-controlled trial to investigate the effects of eplerenone in patients with HIV-associated abdominal fat accumulation

Written informed consent for this protocol will be obtained from all subjects at the first screening visit, prior to any procedures or interventions. In all cases, consent will be witnessed by an appropriate health care professional (investigator/co-investigator staff). All efforts will be made to insure the privacy rights of the subject. No written or oral communication will be made about any subject with anyone other than the subject, unless the subject so requests. Medical information obtained from the study may become part of the subject's permanent hospital record, subject to the confidentiality and privacy regulations of the Massachusetts General Hospital. Subjects will be closely monitored to insure that study participation is not adversely affecting their quality of life, and any adverse events will be reported in a timely fashion and in accordance with the Partners HRC guidelines for adverse event reporting. Kidney function and potassium levels will be serially monitored. If a subject experiences an opportunistic infection or any acute illness, the lifestyle modification program will be held while the subject is acutely ill.

Hyperkalemia is a potential side effect of eplerenone use, and contraindications for the use of eplerenone include serum K > 5.5 mEq/L at initiation. Therefore, any subject with serum K > 5.5 mEq/L at screen will be excluded from the study. During the study, a subject who has an elevated K of > 5.5 mEq/L at any study visit will have a recheck; if the K remains elevated after recheck they will be excluded from the study. Additionally, subjects who experience symptoms of hyperkalemia and have a K > 5.0 mEq/L will be excluded from continued participation in the study. Subjects who have hypotension (SBP < 90) at any study visit after titration to full dose eplerenone 50mg/d will be given a dose reduction to 25 mg/d. If a subject remains hypotensive (SBP < 90) or symptomatic of hypotension at the reduced dose they will be dropped from the study. Since patients with renal insufficiency may require reduced dosing based on creatinine clearance, subjects with renal insufficiency (serum creatinine > 1.5 mg/dl) will also be excluded from participation. Other side effects have been reported and include dizziness, fatigue, diarrhea, headache, stomach pain, cough, breast enlargement or breast enlargement, rash, abnormal vaginal bleeding. Rare but serious side effects include chest pain, tingling in arms and legs, loss of muscle tone, weakness or heaviness in legs, confusion, lack of energy, cold, gray skin or irregular heartbeat. These potential side effects will be assessed for throughout the study.

Exclusion criteria during the study include use of diabetic agents; initiation of ACE-I, ARB, or spironolactone; Hgb < 11; ALT > 2.5 x ULN; persistent hyperkalemia (K > 5.5 mEq/L despite recheck and/or symptoms of hyperkalemia if K > 5.0 mEq/L). If a subject remains hypotensive (SBP < 90) or symptomatic of hypotension after a dose reduction of eplerenone to 25mg for this same reason during the study, they will be dropped from the study.

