#### Interim Safety Visits 1 wk, 2 wks, 4 wks, 2 months and same schedule post 6 month crossover with an additional visit at 10 months

1. Physical exam and interval medical history including blood pressure check
2. Blood: creatinine, K, CBC, ALT
3. Urine pregnancy test of all female subjects

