#### 3 Month Visit

1. Urine pregnancy test for all female subjects
2. Physical exam, including blood pressure check, and medical history

Randomized placebo-controlled trial to investigate the effects of eplerenone in patients with HIV-associated abdominal fat accumulation

3. Euglycemic hyperinsulinemic clamp
4. Bionutrition: DEXA, anthropometric measurements, and review of a session from the lifestyle modification workbook.
5. Fasting blood: lipid profile, HgbA1c, chem. 7, CBC, potassium, creatinine, ALT, CD4/8, viral load, aldosterone, plasma renin activity, inflammatory markers and adipokines: MCP-1, CRP, adiponectin, PAI-1, resistin, TNF $\alpha$ , TNFR2, IL-6, SHBG, total and free testosterone, LH, FSH, estradiol (females only).
6. 24 hour urine will be collected for aldosterone, potassium, sodium, cortisol, and creatinine
7. Optional overnight q 20 minute sampling for growth hormone pulsatility analysis
8. Modifiable activity questionnaire

Oral Glucose Tolerance Test: A standard 75g OGTT will be performed on the morning of the screen visit following a 12 hour fast, with interval measurements of insulin and glucose at 0 and 120 min.

Euglycemic-Hyperinsulinemic Clamp: After 12-h overnight fast, patients will receive a primed infusion of regular insulin mixed with albumin, 80 mU/m^2, for 2 hours, with a variable rate of dextrose administered to maintain blood glucose at 5.0 mmol/L (90 mg/dL). Blood samples will be collected for glucose at time 0 and every 5 min during the 2-hour clamp, and samples for insulin will be collected every 20 min from 0-120 minutes. Insulin sensitivity will be calculated.

Optional GH Pulsatility Analysis: Starting at 2000 until 0740 the next morning, fasting blood will be sampled every 20 minutes. Approximately 1.5cc of blood will be drawn at each time point for a total of 54cc. Mean overnight GH concentration, basal concentration, pulse frequency, pulse amplitude and overall pattern regularity will be determined using the deconvolution analysis and cluster computerized pulsatility program.

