## VI. Biostatistical Analysis

The primary endpoint will be change in insulin stimulated glucose uptake as measured by euglycemic clamp. Secondary endpoints include change in levels of adipokines and endothelial function. In addition, we will assess eplerenone's effects on hepatic fat and IMCL. VAT and SAT will be measured simultaneously and controlled for in the analyses of hepatic fat and IMCL. Randomization will be stratified by gender, age (< or > 45), and BP (SBP >140 or DBP>90, or normotensive). Wilk-Shapiro test will be used to assess for normality of distribution of all variables, and variables that are not normally distributed will be log-transformed. Baseline variables will be compared between treatment groups by t-test for continuous variables and Wilcoxon Rank Sum test for variables that are not normally distributed. Any baseline variable that is statistically different between treatment groups will be adjusted for in subsequent analysis. We will analyze the entire set of repeated measurements (baseline, 3 and 6 mos) by using the longitudinal mixed effects model, using all available data, including interim data from those who do not complete the study, to determine differences in longitudinal mean changes between eplerenone and placebo over 6 mos of treatment (i.e., test for time x group interaction). The analyses will be intention to treat, using all interim data for subjects who do not complete the study. We will control for gender, race, anti-hypertensive and lipid lowering medication use, urine free cortisol, dietary intake (caloric, macronutrient, alcohol, supplements, salt intake), activity, ARV use and smoking. We will analyze the dietary data in terms of overall caloric intake and macronutrient composition, to determine whether there are any differences in diet by study treatment, or whether change in dietary intake patterns, including vitamins, affects the treatment results. Similar analyses will be performed for activity using the Modifiable Activity Questionnaire. In a sensitivity analysis if the dropout rate is higher than expected or differs between groups, we will

Randomized placebo-controlled trial to investigate the effects of eplerenone in patients with HIV-associated abdominal fat accumulation

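### 6-month clamps of removed subjects are not collected, and the only check on that, a conditional LOCF, cannot show whether the loss matters

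*Combined protocol and SAP*

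**What the plan says.** **Removal.** Section IX lists "Exclusion criteria during the study include use of diabetic agents; initiation of ACE-I, ARB, or spironolactone; Hgb < 11", followed by raised ALT and persistent or symptomatic hyperkalaemia. Sections VII and IX both say of a raised potassium that "if the K remains elevated after recheck they will be excluded from the study". Subjects with symptoms and a potassium above 5.0 "will be excluded from continued participation in the study". Those who stay hypotensive or are "symptomatic of hypotension at the reduced dose they will be dropped from the study". For potassium and blood pressure, removal from the study is explicit. For new medicines, haemoglobin and ALT it is the natural reading of the list's label.

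**Visits.** Section V schedules the clamp at baseline and at 3, 6 and 12 months. It describes no early-termination or post-removal visit, and the Data Safety Monitoring Plan describes assessment only while a patient is participating. Before month 3 the schedule is "Interim Safety Visits 1 wk, 2 wks, 4 wks, 2 months and same schedule post 6 month crossover", with "Blood: creatinine, K, CBC, ALT". Glucose-related tests are first repeated at the 3-month visit ("Fasting blood: lipid profile, HgbA1c, chem. 7, CBC, potassium, creatinine, ALT"), which also has a clamp.

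**Analysis.** Section VI specifies a longitudinal mixed model on baseline, 3- and 6-month data and states: "The analyses will be intention to treat, using all interim data for subjects who do not complete the study". The primary comparison is at 6 months. LOCF is a sensitivity analysis, run if dropout is above expectation (no rate is given) or unequal between arms. Its stated purpose is to find out whether dropouts changed the result.

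**The concern.** A likelihood-based mixed model gives a valid 6-month comparison for subjects without a 6-month clamp only if, given their observed clamps and the covariates, their unseen values behave like those of similar subjects who stayed. The plan does not state this assumption. Two features make the question reasonable here. Starting a diabetic agent is plausibly connected with glucose uptake, the primary endpoint. Section VII names hyperkalaemia and hypotension as reactions to eplerenone, so removal may differ by arm. Potassium, blood pressure during follow-up, haemoglobin and ALT are not among the model covariates in Section VI.

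A clamp that was never done cannot be recovered at analysis. The sensitivity analysis must then show how much the missing values could matter, and a single imputation rule gives one alternative answer, not a range.

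**Working it through.** **1. The plan's own figure.** With 25 evaluable per arm, a difference of 0.8 SD and a two-sided 5% t-test, exact power is 79.1% (normal approximation 80.7%), so the stated 80% reproduces. The plan's 1.4 mg/kg/min over its SD of 1.7 is 1.4/1.7 = 0.82 SD. The standard error of the difference is √(2/25) = 0.283 SD.

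**2. Assumptions (not in the documents).** Removal before the 6-month clamp: 12% in one arm, 4% in the other. Clamps at 0, 3 and 6 months are normal with SD 1 (= 1.7 mg/kg/min), equal correlation 0.5 or 0.7, and no mean trend. A share of removals depends on glucose uptake, at log-odds 1 or 2 per SD worse; the rest are random. Removal falls before or after month 3. Each case was simulated with 1.5 million subjects per arm. A positive bias favours the arm with more removals; exchanging the arms reverses it.

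**3. Bias in the 6-month difference.**

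| What drives removal | Mixed model (SD) | LOCF (SD) |
|---|---|---|
| Unseen 6-month value, one third of removals | 0.01 to 0.03 | 0.01 to 0.02 |
| Unseen 6-month value, half of removals | 0.02 to 0.04 | 0.01 to 0.02 |
| Unseen 6-month value, all removals | 0.03 to 0.08 | 0.02 to 0.04 |
| Observed 3-month clamp, all removals | 0.00 | −0.02 to −0.04 |

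If 4% in both arms are endpoint-driven and a further 8% in one arm are random, the mixed-model bias is 0.00.

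In mg/kg/min: 0.011 × 1.7 = 0.02 and 0.031 × 1.7 = 0.05 for one third; 0.083 × 1.7 = 0.14 at the upper end. Against the 1.4 target, 0.05/1.4 = 4% and 0.14/1.4 = 10%.

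**4. What LOCF can tell.** When every removal depends on the unseen value, LOCF lies 0.01 to 0.04 SD below the biased mixed model. When every removal depends on the observed clamp, LOCF lies 0.02 to 0.04 SD below an unbiased mixed model. The gap has the same sign and about the same size in both cases.

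**5. Consequence for the test.** A bias of 0.03 SD is 0.03/0.283 = about a tenth of a standard error. Against eplerenone it lowers power from 79% to 76% (d = 0.77); in its favour, type I error is 5.1%. The 0.08 SD corner gives 70% (d = 0.72) and 5.9%.

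**6. What a delta grid would cover.** With shifts up to 1 SD in the missing values, the same shift in both arms moves the difference by (0.12 − 0.04) × 1 = 0.08 SD. Opposite shifts move it by (0.12 + 0.04) × 1 = 0.16 SD, or 0.16 × 1.7 = 0.27 mg/kg/min. This spans the upper case in step 3.

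**7. Cost of collecting off-drug clamps.** If the 12% removed are on eplerenone and lose all benefit, the difference becomes 0.88 × 0.80 = 0.70 SD. Arms of 25/0.88 = 28 and 25/0.96 = 26 then give power of about 72%, against 79%.

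**The case against.** The strongest case against is that this is too small to matter. On the plausible rows the bias is about a tenth of a standard error, and even that needs removal that is both unequal between arms and dependent on the unseen value. Nothing in the documents links removals for potassium, blood pressure, haemoglobin or ALT to glucose uptake. A diabetic agent started on study results would usually follow the 3-month clamp, and when removal depends on that clamp the mixed model is unbiased. What remains is an agent started outside the study or on deterioration after month 3. At 28 and 26 per arm, 12% and 4% are about three subjects and one. The smallest significant difference is about 0.57 SD, so a grid movement of 0.08 to 0.16 SD matters only for a borderline result. All of this stands and limits the weight of the point.

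It is also fair that the second LOCF trigger works: a difference in dropout between arms can be checked without an expected rate. Only the first trigger lacks its reference value. This does not rescue LOCF, because step 4 concerns what it shows once it has run.

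The scale is approximate. The 1.7 is given as the SD of glucose uptake, not of change. At correlation 0.5 the SD of change equals it (√(2 × 0.5) = 1). At 0.7 it is √(2 × 0.3) = 0.77 of it, or 1.32 mg/kg/min. On that scale the largest 0.7 results become 0.022/0.77 = 0.03 (one third) and 0.060/0.77 = 0.08 (all), so the upper ends do not change.

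A reader might infer that removed subjects are dropped from the analysis, or that the intention-to-treat statement is breached. Section VI says the opposite: their interim data stay in. A reader might also assume high removal with full loss of benefit and conclude that power collapses. The documents give no removal rate, and such figures would reflect the assumption alone. Consent wording was not in the text reviewed, so follow-up described there cannot be ruled out.

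**Conclusion.** The point holds in a limited form and is worth considering. Removal is from the study, no later clamp is provided, and the 6-month comparison therefore relies on missing at random for removed subjects. LOCF cannot do the job the plan gives it: it replaces one assumption with another, and its distance from the mixed model does not separate a biased result from an unbiased one.

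The documents do not show that the trial is or will be biased. On the assumed 12% against 4% removal, correlations of 0.5 to 0.7 and log-odds of 1 to 2 per SD, the bias is about 0.01 to 0.03 SD if a third of removals depend on the unseen value, and at most 0.08 SD if all do. It is zero if removal depends on the observed clamp, is unrelated to the endpoint, or is endpoint-related to the same degree in both arms. The reading of the text is secure; the size rests on the assumptions.

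**What to change.** **Main change.** Replace the conditional LOCF with a delta-adjusted sensitivity analysis that is always run. Missing 6-month clamps are imputed under the primary model and then shifted, separately by arm, over a grid fixed in advance, for example 0 to 1 SD (0 to 1.7 mg/kg/min) in either direction. Report the difference and interval across the grid, and the shift, if any, at which the conclusion changes. No expected dropout rate is then needed. The cost is one extra analysis and no new data. It does not test missing at random; it shows how far the answer depends on it.

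**Secondary option, consistent with the intention-to-treat label.** Leave every drug-stopping, dose and medication rule as it is. Distinguish stopping study drug from ending outcome collection, and invite removed subjects, with consent and where the investigator judges it medically acceptable, to the 3- and 6-month endpoint visits already scheduled. Report results with and without values obtained off drug or after a new medicine.

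This option costs more. It needs an amendment to the removal wording and to the consent. Each retained visit brings about a week of high-sodium diet and a two-hour clamp with glucose sampled every five minutes; Section VII repeats the haemoglobin exclusion under blood drawing, so acceptability is a real question. Off-drug values also dilute the effect: about 0.70 instead of 0.80 SD, and power of about 72% against 79%, if 12% on eplerenone lose all benefit. They answer a treatment-policy question, whereas Section I sets out to test mineralocorticoid receptor blockade itself. The plan should say which effect it wants before choosing this option. Values after a new glucose-lowering medicine would remain hard to interpret.

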### **Data Safety Monitoring Plan**

Prior to the start of study, a data safety monitoring board will be created and this board will consist of a statistician, a clinician not directly related to the research project, but one who is familiar with HIV infection and its complications, and a member of the HIV community. This board will meet quarterly to review any potential side effects or adverse events in relation to the use of eplerenone or participation in the study. The DSMB will meet and review adverse events in accordance with the guidelines of the Massachusetts General Hospital Human Research Committee. Reports generated by

Randomized placebo-controlled trial to investigate the effects of eplerenone in patients with HIV-associated abdominal fat accumulation

the DSMB will be submitted to the Partners Institutional Review Board when otherwise indicated or requested.

The principal investigator and/or co-investigator will be responsible for following patients during the study. Patients will be assessed at every visit during their study participation. The investigators and study staff will assure that all CRFs, source documents and informed consent are accurate and complete after each study visit.

